**Table 2. Description of intervention sessions**

Session #	Session name	Session description	Social support person invited to session?
1	Introduction	
 
Aim: Present information on the intervention program (duration, content, expectations)
 
Separate, 50-min group sessions will be held with participating MAT clients and social support persons identified. The social support person introduction session will be held two weeks after the MAT client session.
 
	Yes
2	Working in a social network-based context	
 
Aim: Identify, recruit, and maintain a network supportive of positive change
 
In this 50-min session, the counselor will explain the importance of social support in achieving positive outcomes, identify the primary goals for which the client will focus on in the program, identify people who can provide the client with positive support using social network mapping, plan and rehearse contacting potential social
 
	No

		support persons, plan for activities with social support persons and maintenance of social network support.	
3	Setting drinking and drug use goals	
 
• Aim: Understand the client's current substance use, establish substance use harms, and agree on where the client would like to be in relation to their substance use
 
• In this 50-min session, the counselor will get an account of recent substance use behavior, elicit concerns about the behavior and its consequences (change talk), explore motivation to change and self-efficacy for achieving a change plan, agree on a change plan (commitment talk)
 
	Yes
4	Coping skills 1	
 
• Aim: Identify high-risk situation for drinking and drug use and agree on a coping strategy for each situation
 
• In this 50-min group session with other MAT clients, the counselor will provide information on the nature of high-risk situations, help the clients to brainstorm potential coping strategies, and interactively practice coping in high-risk situations
 
	No
5	Coping skills 2	
 
• Aim: Identify high-risk situation for drinking and drug use and agree on a coping strategy for each situation
 
• In this second 50-min session on coping skills, the counselor will work with clients and their social support persons to discuss to create an individualized network-based coping strategy
 
	Yes
6	Making lifestyle changes	
 
• Aim: Establish a lifestyle, free of alcohol and drug problems, with network support
 
• In this 50-min session, the counselor will establish an understanding of an alcohol/drug problem-free lifestyle based on the vision of the MAT client and their social support persons, identify roles in achieving new routines and activities, create an action plan (with weekly schedule for routine activities, including income generation), and use problem-solving to address challenges to the plan
 
	Yes
7	Generating income	
 
• Aim: Build income-generating skills
 
• In this 3-hour group session with other MAT clients and social support persons, the facilitator(s) will lead hands-on training on income-generating skills, including construction, carpentry, cooking, and jewelry-making.
 
	Yes

Participant attendance will be recorded for each session. Members of the study team will observe sessions and take notes on intervention fidelity and delivery using a semi-structured form. After each session, participants will be asked to complete a brief exit survey to assess satisfaction with the session. The exit survey will be administered by the intervention counselor. At the end of the pilot, the study team will conduct a post-intervention survey with MAT client participants and their participating social support persons. The post-intervention survey will include similar questions to the baseline survey but will also include questions to gauge acceptability and satisfaction with the intervention, experiences with social and income-generating activities, and suggestions for changes to the intervention. The post-intervention survey is expected to last between 15 minutes (for social support persons) and 20 minutes (for MAT clients).

We will also conduct 25 follow-up qualitative, in-depth interviews with 10 MAT client participants, 10 social support person participants, and all 5 intervention counselors, about one month after the trial. We will purposively sample participant based on their attendance in sessions and based on responses to survey questions, so that we can obtain a sample of individuals with various experiences with the program. Study interviewers will use a semi-structured interview guide to facilitate the discussion. The

guide will include questions on experiences with the program (what worked and what could be improved), how well counselors followed the intervention manual, what clients learned, how clients incorporated lessons learned in their daily lives, and changes in the quality of relationships with social support persons and other people in their lives. Interviews are expected to last about 45 minutes and will be audio-recorded with participant permission.

2. *Describe the number and type of study visits and/or contacts between the study team and the participant, how long they will last, and where/how they will take place.*

**Stage 1:** All participants will be in contact with the study team for recruitment purposes. For Phase 1, key informant interviews are expected to last between 45m and 1h. Phase 1 participants will participate in a single key informant interview. It is possible that health providers or CBO staff who are interviewed for Phase 1 will be invited to the key stakeholder workshop for Phase 5. For Phase 3, focus groups are expected to last 1.5 to 2h. Each focus group participant will participate in just one focus group discussion. The informed consent process for key informant interviews and focus groups will take place before the interview or the focus group and is expected to last no more than 10m. Key stakeholder workshops will last 4 to 5h.

Key informant interviews will take place in a private and quiet location, either at the study office, the CBO office, or the provider office at the MAT clinic. Focus groups will take place in the conference room of the building that houses the study office located near the Muhimbili MAT clinic on the grounds of the Muhimbili National Hospital. The key stakeholder workshops will take place in rented venues (conference rooms) in either Dodoma (where many government offices are located, including the Ministry of Health) or Dar es Salaam.

**Stage 2:** All pilot participants will be in contact with the study team for recruitment purposes, for pre- and post-intervention surveys, and through the pilot intervention. Upon enrollment, the pre-intervention survey is expected to take 20m to complete for enrolled MAT clients and 15m for enrolled social support persons. MAT clients will participate in six 50-min sessions and one 3h session over the course of six weeks. Social support persons will participate in four 50-min sessions and one 3h session over the course of six weeks. After each intervention session, participants will complete a 5m exit survey. The post-intervention survey is expected to take 20 minutes and 15 minutes for MAT clients and social support persons to complete, respectively, and will be conducted a week after the intervention ends. A select number of pilot participants will also be in contact with the study team for an approximately 45m follow-up, in-depth interview one month after their last intervention session.

3. *Describe the expected duration of the study from the perspective of the individual participant and duration overall.*

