**Stage 2:** We will use descriptive statistical methods and qualitative data analysis to examine intervention acceptability and fidelity of the intervention. Enrollment data will be used to describe the characteristics of the MAT clients and their social support persons. We will calculate the proportion of sessions attended. We will explore the reasons for missed sessions. These data will provide important information on the characteristics of study participants, the dose of the intervention, retention, reasons for missed sessions, and the acceptability of session content and approach. We will examine key outcomes such as changes in knowledge and attitudes, and changes in network and social engagement.

5. **Answer the following if they are relevant to your study design:**

- A. *If the study has different arms, explain the process for assigning participants (intervention/control, case/control), including the sequence and timing of the assignment.*

N/A

- B. *If human biospecimens (blood, urine, saliva, etc.) will be collected, provide details about who will collect the specimen, the volume (ml) and frequency of collection, how the specimen will be used, stored, identified, and disposed of when the study is over. If specimens will be collected*

for use in future research (beyond this study), complete the “Biospecimen Repository” section below.

N/A

- C. If genetic/genomic analyses are planned, address whether the data will be contributed to a GWAS or other large dataset. Address returning unanticipated incidental genetic findings to study participants.

N/A

- D. If clinical or laboratory work will be performed at JHU/JHH, provide the JH Biosafety Registration Number.

N/A

- E. If you will perform investigational or standard diagnostic laboratory tests using human samples or data, clarify whether the tests are validated and/or the lab is certified (for example is CLIA certified in the U.S.). **For clinical tests of human biospecimens, no results may be returned unless completed in a certified lab.** Explain the failure rate and under what circumstances you will repeat a test. For all human testing (biomedical, psychological, educational, etc.), clarify your plans for reporting test results to participants and/or to their families or clinicians. Address returning unanticipated incidental findings to study participants.

N/A

- F. If your study involves medical, pharmaceutical or other therapeutic intervention, provide the following information:

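### Counselors administer the exit survey on the sessions they deliver, so the only session-by-session self-report of satisfaction is at risk of upward courtesy bias

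*Protocol*

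**What the plan says.** Protocol section V.C.1 (Study Implementation, Stage 2) describes the session-level data in the text after Table 2:

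- Attendance: "Participant attendance will be recorded for each session".
- Observation: "Members of the study team will observe sessions and take notes on intervention fidelity and delivery using a semi-structured form".
- Satisfaction: "After each session, participants will be asked to complete a brief exit survey to assess satisfaction with the session".
- Who collects the satisfaction rating: "The exit survey will be administered by the intervention counselor".

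Table 2 has the counselor running sessions 2 to 6. In session 5, for example, "the counselor will work with clients and their social support persons to discuss to create an individualized network-based coping strategy". Session 7 is different: "the facilitator(s) will lead hands-on training on income-generating skills". The entry for session 1 names no leader. The follow-up interviews are to include "all 5 intervention counselors".

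The same section gives the other participant measures to other people. The study team conducts the post-intervention survey, and study interviewers conduct the in-depth interviews. Section V.C.4 says the Stage 2 data will inform, among other things, "reasons for missed sessions, and the acceptability of session content and approach". SAP section II covers acceptability and feasibility as the primary outcomes. It lists completion, attendance at individual sessions, losses and withdrawals, qualitative themes and counselor-reported fidelity. It does not mention the exit survey.

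**The concern.** A participant who has just finished a session is asked how satisfied they were, and the survey is administered by a counselor. For most sessions Table 2 has a counselor delivering the content as well. People tend to be polite in that position. The pressure may be greater here: clients enter the pilot because of a recent positive drug or alcohol test, and in session 3 the counselor takes an account of their recent use. The counselors are also trained and supervised weekly by a co-PI who is a psychiatrist at the clinic where the clients receive methadone (Safety Monitoring section).

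At stake is the diagnostic use of the ratings. The pilot tests an adapted seven-session program, and one natural product is a view of which sessions worked less well. The exit survey is the only instrument that asks every attendee about each session at the time. If most ratings sit near the top for reasons of courtesy, a weak session is harder to see.

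**Working it through.** The documents give no figure for the exit survey, so there is nothing to reproduce. The check has three parts.

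**1. How many surveys are affected**

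Inputs: 20 MAT clients and 20 to 60 social support persons (section III.B); 7 sessions per client and 5 per support person (Table 2 and section IX.B); support persons invited to sessions 1, 3, 5, 6 and 7 (Table 2). Full attendance is assumed.

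All counselor-administered surveys = participants × sessions:
- clients: 20 × 7 = 140
- support persons: 20 × 5 = 100 to 60 × 5 = 300
- total: 140 + 100 = 240 to 140 + 300 = 440

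Surveys after sessions where Table 2 names the counselor as leader (sessions 2 to 6; support persons attend 3, 5 and 6 of these):
- clients: 20 × 5 = 100
- support persons: 20 × 3 = 60 to 60 × 3 = 180
- total: 100 + 60 = 160 to 100 + 180 = 280

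The second range is where the conflict is clearest. The documents do not say whether the session 7 facilitators are also counselors.

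**2. What courtesy bias would do (illustration only)**

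Let p be the true proportion satisfied and b the share of dissatisfied respondents who report satisfaction. Observed satisfaction is then p + b(1 − p). Neither p nor b is in the documents; the values below are assumptions.

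| True p | b = 0.10 | b = 0.25 | b = 0.50 |
|---|---|---|---|
| 0.60 | 0.64 | 0.70 | 0.80 |
| 0.70 | 0.73 | 0.775 | 0.85 |
| 0.80 | 0.82 | 0.85 | 0.90 |

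The upward shift runs from 2 points (0.82 − 0.80) to 20 points (0.80 − 0.60). If b is the same in every session, the gap between two sessions shrinks by the factor 1 − b. A true gap of 20 points (0.60 against 0.80) is observed as 18 points (0.64 against 0.82), 15 points (0.70 against 0.85) or 10 points (0.80 against 0.90).

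For scale, the exact (Clopper-Pearson) 95% interval for 14 of 20 clients satisfied (70%) is 46% to 88%. Comparisons between sessions are imprecise in any case, and compression of the gaps makes them harder still.

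**3. What other sources cover the same question**

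| Source | Collected by | Level |
|---|---|---|
| Exit survey | Intervention counselor | Each session, self-reported satisfaction |
| Attendance | Recorder not stated | Each session, behavior |
| Observation form | Study team | Session, fidelity and delivery |
| Post-intervention survey | Study team | Whole intervention, a week after it ends |
| In-depth interviews | Study interviewers | 10 clients, 10 support persons and 5 counselors, about a month later |

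Only the first row is a participant's own rating of a given session, and it is the one participant survey or interview that the protocol assigns to counselors.

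**The case against.** The strongest reply is that little depends on this survey. It is absent from the SAP, and no threshold or decision rests on it. Section V.C.4 does not name it either; the data listed just before its reference to acceptability are enrollment, attendance and reasons for missed sessions. The post-intervention survey, run by the study team, asks about satisfaction and suggested changes. The interviews ask what could be improved and sample participants partly by attendance, so low attenders can be included. This stands, and it limits the consequence.

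Three stronger readings are tempting, and the documents do not support them.

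- A reader might infer that this is the only session-level measure of acceptability, so that a primary outcome is compromised. Attendance is recorded per session, and SAP section II places it under acceptability and feasibility. Attendance is an imperfect signal of liking the content, because each session carries a payment of 10,000 shillings (section IX.B), but it is a listed measure.
- A reader might infer that the ratings are biased upward as a matter of fact. Only a risk is supported. The protocol does not say whether the counselor reads the items aloud or hands out a form, or whether the counselor who led the session is the one who collects it. The rating is of the session, not of the counselor by name.
- A reader might infer that counselors are clinic staff on whom clients depend. This is not stated. Sessions take place at the study or CBO office, participants are told they may decline questions and withdraw without penalty (section VII.B), and support persons are not shown to depend on the clinic.

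The last point weakens the argument from dependence. It does not remove ordinary courtesy toward the person who has just run the session, and no safeguard is described.

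**Conclusion.** The concern holds as a risk to one instrument. The only session-level self-report of satisfaction is administered by counselors, who deliver at least sessions 2 to 6, with no stated anonymity. The likely direction of bias is upward, and its size cannot be derived from the documents. At full attendance it touches 240 to 440 surveys, with the clearest conflict in 160 to 280. These counts rest on five sessions per support person; section V.C.3 describes five weekly sessions plus the three-hour session for them, which does not agree with Table 2.

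The outcomes listed in the SAP do not depend on the survey, and acceptability of the whole intervention can still be judged from other sources. What is weakened is the ability of the exit ratings to show which sessions need revision. That is worth correcting because the remedy is small.

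**What to change.** In section V.C.1, replace the sentence on administration with wording to this effect: participants complete the exit survey themselves under study ID only and return it in a sealed envelope or box; where a study-team observer is present, the observer may instead hand it out or read it aloud, out of the counselor's hearing; individual responses are not shown to the counselor.

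The cost is one protocol sentence, a change to the session procedure, and envelopes or a box. The survey stays at about 5 minutes (section V.C.2) and no visit is added. There are two practical limits. Participants with low literacy need a study-team member who is not a counselor to read the items. The protocol says study-team members observe sessions but does not say that every session is observed, so some staff time may have to be arranged for unobserved sessions.

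If the sessions are already complete, nothing can be changed in the data. The report should then state that counselors administered the exit survey and give this as a limitation of the satisfaction ratings.

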**Stage 1:**

Phase 1: Key informant interviews are expected to last 45m to 1h.

Phase 3: Focus group discussions are expected to last 1.5 to 2h.

Phase 5: Key stakeholder meetings are expected to last 4 to 5h.

**Stage 2:**

MAT client participants: Six weeks, as well as a 45-minute, follow-up interview for select participants

- Pre-intervention survey: Approximately 20m

- Intervention: 50-min intervention session weekly for six weeks plus a 3h interactive, income-generating skills-building session
- Post-intervention survey: Approximately 20m
- Post-intervention interview: Approximately 45m (select participants)

Social support person participants: 6 weeks, as well as a follow-up interview for select participants

Pre-intervention survey: Approximately 15m

- Pre-intervention survey: Approximately 15m
- Intervention: 50m intervention session weekly for five weeks plus a 3h interactive, income-generating skills-building session
- Post-intervention survey: Approximately 20m
- Post-intervention interview: Approximately 45m (select participants)

The overall duration of the study (Stages 1 and 2) will be two years.

4. *Provide a brief data analysis plan and a description of variables to be derived.*

**Stage 1:** We will analyze interview, focus group, and stakeholder meeting transcripts using framework analysis. Transcript data will be coded in NVivo and broadly categorized into participant feedback on the different intervention components with more detailed subcategories of codes and topics (such as content, feasibility and acceptability, and delivery) developed within these broader categories based on the data. Each interview will be placed into a framework developed from the broad and more detailed categories of responses, using a template developed in Microsoft Excel. Two independent coders will enter each interview/focus group into the framework and any discrepancies will be discussed and resolved. The final framework will be shared with data collectors and other study team members for discussion and to inform decisions on adaptations to the B-SBNT intervention. The study team will adapt the existing intervention manual and materials based on findings from Phases 1-4. Topical experts and other key stakeholders will provide feedback on drafts of the adapted manual and materials, which the study team will integrate in Phase 6. We will then pilot the resulting adapted intervention in Stage 2.

**Stage 2:** We will use descriptive statistical methods and qualitative data analysis to examine intervention acceptability and fidelity of the intervention. Enrollment data will be used to describe the characteristics of the MAT clients and their social support persons. We will calculate the proportion of sessions attended. We will explore the reasons for missed sessions. These data will provide important information on the characteristics of study participants, the dose of the intervention, retention, reasons for missed sessions, and the acceptability of session content and approach. We will examine key outcomes such as changes in knowledge and attitudes, and changes in network and social engagement.

5. **Answer the following if they are relevant to your study design:**

- A. *If the study has different arms, explain the process for assigning participants (intervention/control, case/control), including the sequence and timing of the assignment.*

N/A

- B. *If human biospecimens (blood, urine, saliva, etc.) will be collected, provide details about who will collect the specimen, the volume (ml) and frequency of collection, how the specimen will be used, stored, identified, and disposed of when the study is over. If specimens will be collected*

for use in future research (beyond this study), complete the “Biospecimen Repository” section below.

N/A

- C. If genetic/genomic analyses are planned, address whether the data will be contributed to a GWAS or other large dataset. Address returning unanticipated incidental genetic findings to study participants.

N/A

- D. If clinical or laboratory work will be performed at JHU/JHH, provide the JH Biosafety Registration Number.

N/A

- E. If you will perform investigational or standard diagnostic laboratory tests using human samples or data, clarify whether the tests are validated and/or the lab is certified (for example is CLIA certified in the U.S.). **For clinical tests of human biospecimens, no results may be returned unless completed in a certified lab.** Explain the failure rate and under what circumstances you will repeat a test. For all human testing (biomedical, psychological, educational, etc.), clarify your plans for reporting test results to participants and/or to their families or clinicians. Address returning unanticipated incidental findings to study participants.

N/A

- F. If your study involves medical, pharmaceutical or other therapeutic intervention, provide the following information:

- a. Will the study staff be blind to participant intervention status?

N/A

- b. Will participants receive standard care or have current therapy stopped?

N/A

- c. Will you use a placebo or non-treatment group, and is that justifiable?

N/A

- d. Explain when you may remove a participant from the study.

N/A

- e. What happens to participants on a study in which there is a medical intervention when the study ends? Will participants continue to have access to the study intervention? What happens if they leave the study early?

N/A

- f. Describe the process for referring participants to care outside the study, if needed.

N/A

**VI. Data Custody, Management, Security, and Confidentiality Protections:** *Data security and management plans must meet institutional standards. If you need assistance, contact [jhspc\\[contact]](mailto:[contact]).*

*Investigators are responsible for ensuring the security of data from the time of collection, through any transfers from one system to another, analysis, sharing, storage, and ultimate archiving and disposal. The questions below seek to elicit your plans for these protections. Feel free to add information.*

**1. Data Sources:** Identify the source(s) of data.

- Participant/Parent-Guardian/Legally Authorized Representative
- JHM medical records (from Epic)

*Note: Please complete the **Data Trust Risk Tiers Calculator** available on the Applications and Forms page on the JHSPH IRB website: <https://www.jhsph.edu/offices-and-services/institutional-review-board/applications-and-forms/>, and upload a copy of the those documents to the “Miscellaneous” section of your PHIRST application. In addition, review the Data Protection Attestation for Research and/or Healthcare Operations at the link below and certify your attestation of compliance to those requirements: [https://intranet.insidehopkinsmedicine.org/privacy\\_office/\\_docs/additional\\_information/Data%20Protection%20Attestation.pdf](https://intranet.insidehopkinsmedicine.org/privacy_office/_docs/additional_information/Data%20Protection%20Attestation.pdf).*

